#### **Progression free survival (PFS)**

PFS is defined as the time from the date of start of treatment to the date of the first documented progression according to RECIST 1.1, or death due to any cause. Clinical deterioration without objective radiological evidence will not be considered as documented disease progression.

PFS will be summarized using the KM method, based on FAS. Median PFS, with corresponding 95% CI, and 25th and 75th percentiles ([Brookmeyer and Crowley 1982](#), [Klein and Moeschberger 1997](#)) will be presented. KM estimates for PFS proportions at specific timepoints (3, 6, 9, 12, and 18

months), along with 95% CI (Greenwood's formula, [Kalbfleisch and Prentice 2002](#)) will also be provided. The number (%) of events and subjects censored will also be summarized.

Participants who had never received one of the investigational drugs will be excluded from the PFS analysis.

PFS will be censored at the date of the last adequate tumor assessment prior to the earliest of analysis cut-off date, the start of a subsequent anti-neoplastic therapy (if any), if the event occurred after two or more missing tumor assessments, or study treatment discontinuation before radiological progression or death (for patients who discontinued study treatment before radiological progression/death and also prior to the approval of protocol version 01, PFS will be censored at the date of the last adequate tumor assessment prior to the approval of protocol version 01). The date of last adequate tumor assessment is the date of the last tumor assessment with overall lesion response of CR, PR or SD before an event or a censoring reason occurred. If no post-baseline assessments are available (before an event or a censoring reason occurred), the date of enrollment will be used. If a subject has no progression or death, the subject is censored at the date of last adequate tumor assessment.

The number of subjects censored and reasons for censoring will be summarized using descriptive statistics.

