Source Data/Document	Source data refers to the initial record, document, or primary location from where data comes. The data source can be a database, a dataset, a spreadsheet or even hard-coded data, such as paper or eSource
Stage of cancer	The extent of a cancer in the body. Staging is usually based on the size of the tumor, whether lymph nodes contain cancer, and whether the cancer has spread from the original site to other parts of the body
Start of the clinical trial	The start of the clinical trial is defined as the signature of the informed consent by the first subject
Study treatment	Any single drug or combination of drugs or intervention administered to the subject as part of the required study procedures
Study treatment discontinuation	When the subject permanently stops taking any of the study drug(s) prior to the defined study treatment completion date (if any) for any reason; may or may not also be the point/time of study discontinuation
Subject	A trial participant (can be a healthy volunteer or a patient depending on the study design)
Subject number	A unique number assigned to each subject upon signing the informed consent form. This number is the definitive, unique identifier for the subject and should be used to identify the subject throughout the study for all data collected, sample labels, etc.

Treatment arm/group	A treatment arm/group defines the dose and regimen or the combination, and may consist of 1 or more cohorts.
Variable	A measured value or assessed response that is determined from specific assessments and used in data analysis to evaluate the drug being tested in the study
Withdrawal of study consent (WoC)	Withdrawal of consent from the study occurs only when a subject does not want to participate in the study any longer and does not allow any further collection of personal data

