## Amendment 1 (13-Oct-2021)

### Amendment rationale

The main purpose of this protocol amendment is to modify the study conduct and data analysis following the sponsor's decision to halt study enrollment on 28-Jul-2021, as communicated to Health Authorities as per local requirements. The enrollment halt decision was based on lack of tolerability observed in capmatinib and spartalizumab combination treatment in the run-in part (Part 1) of the trial.

Immediately following the enrollment halt, below procedural changes have been performed:

- All ongoing subjects were discontinued from spartalizumab treatment and continue to receive single agent capmatinib, given the proven tolerability and efficacy of capmatinib monotherapy in this study indication.
- Enrolled subjects who had not started study treatment were to receive capmatinib single agent treatment from the start

Final | Due to the change in the study treatment following spartalizumab discontinuation, this study can no longer appropriately assess the clinical activity of the combination. Therefore, data collection requirements will be simplified and the study objectives will be updated, as follows:

- The centralized review of study imaging which was put in place to provide blinded and independent efficacy assessment of the combination treatment is no longer required.
- As blinded and independent tumor assessments will no longer be performed, the primary endpoint of the study will be amended to ORR by investigator assessment as per RECIST 1.1, [REDACTED]. The primary endpoint analysis will be based on the estimation of ORR and hypothesis testing of ORR will not be performed.
- PFS and DCR by investigator assessment will be the study secondary endpoints. PFS will be reported using Kaplan Meier analysis. [REDACTED]

The secondary estimand constructed for DOR is no longer applicable.

- In order to capture any potential delayed treatment effect of the combination, BOR and PFS will take into account all available tumor assessments irrespective of spartalizumab discontinuation due to any reason including sponsor decision. The intercurrent events of the primary estimand were updated accordingly.

- [REDACTED]
- [REDACTED]

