## Progression free survival (PFS)

The analysis in this section refer to the PFS as per local investigator assessment for Part 1.

PFS is defined as the time from the date of start of treatment (Part 1) to the date of the first documented progression according to RECIST 1.1, or death due to any cause. If a subject has no progression or death, the subject is censored at the date of last adequate tumor assessment. Definition of last adequate tumor assessment is provided in [Appendix 1](#).

PFS will be summarized using the KM method, based on FAS. Median PFS, with corresponding 95% CI, and 25th and 75th percentiles ([Brookmeyer and Crowley 1982](#), [Klein and Moeschberger 1997](#)) will be presented. KM estimates for PFS proportions at specific timepoints, along with 95% CI ([Greenwood's formula](#), [Kalbfleisch and Prentice 2002](#)) will also be provided.

Participants who did not receive one of the investigational drugs will be excluded from the PFS analysis.

PFS will be censored at the date of the last adequate tumor assessment prior to the earliest of analysis cut-off date, the start of a subsequent anti-neoplastic therapy (if any), if the event occurred after two or more missing tumor assessments, or study treatment discontinuation before radiological progression or death. Clinical progression without objective radiological evidence will not be considered as documented disease progression. The date of last adequate tumor assessment is the date of the last tumor assessment with overall lesion response of CR, PR or SD before an event or a censoring reason occurred. If no post-baseline assessments are available (before an event or a censoring reason occurred), the date of enrollment will be used.

The number of subjects censored and reasons for censoring will be summarized using descriptive statistics.

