##### **16.1.4.5.1 Calculation of 'time to event' variables**

Time to event = end date - start date + 1 (in days)

When no post-baseline tumor assessments are available, the date of randomization/start of treatment will be used as end date (duration = 1 day) when time is to be censored at last tumor assessment, i.e. time to event variables can never be negative.

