#### 2.1.1 General definitions

##### 2.1.1.1 Investigational drug and study treatment

**Investigational drug** will refer to capmatinib or spartalizumab. The terms investigational drug and study drug are used interchangeably.

**Study treatment** will refer to capmatinib + spartalizumab.

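### The PFS censoring trigger, study treatment discontinuation, is not reconciled across the documents: the glossary counts a spartalizumab-only stop, while the amendment says PFS ignores it

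*SAP*

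**What the plan says.** **Trigger.** Protocol 12.5.2.1 and SAP 2.7.1 censor Part 1 PFS at the last adequate tumor assessment before the earliest of several events, one of which is stopping study treatment without a prior PFS event. The SAP wording, quoted in part, is "study treatment discontinuation before radiological progression or death (for patients who discontinued study treatment before radiological progression/death and also prior to the approval". Its parenthesis, which the protocol lacks, covers subjects who discontinued before approval of protocol version 01: they are censored at the last adequate assessment before that approval.

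**Definition.** The protocol glossary describes study treatment discontinuation thus: "When the subject permanently stops taking any of the study drug(s) prior to the defined study treatment completion date (if any) for any reason". SAP 2.1.1.1 says that study treatment "will refer to capmatinib + spartalizumab".

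**Intent.** The amendment rationale states: "BOR and PFS will take into account all available tumor assessments irrespective of spartalizumab discontinuation due to any reason including sponsor decision". Protocol 12.4.1.3 and SAP 2.5.3 carry this into the analysis text for BOR. Neither PFS section carries it.

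**Fallback date.** In both PFS sections: "If no post-baseline assessments are available (before an event or a censoring reason occurred), the date of enrollment will be used". Appendix 1 of the protocol (16.1.3.2.8 and 16.1.4.5.1) uses randomization or start of treatment instead, gives a duration of 1 day, and adds that "time to event variables can never be negative".

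**The concern.** Immediately after the enrollment halt of 28-Jul-2021 the sponsor stopped spartalizumab in all ongoing subjects, who continued on capmatinib alone. By the glossary, that is study treatment discontinuation. A programmer who takes the trigger from the glossary would therefore censor event-free combination subjects because of a sponsor decision and leave out later progressions and deaths on capmatinib. The amendment says the opposite should happen. The later Kaplan-Meier landmarks (12 and 18 months in SAP 2.7.1) depend most on that follow-up, and PFS is the only time-to-event efficacy endpoint left among the Part 1 primary and secondary endpoints.

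The fallback date is a second, separate slip in the same paragraph. The glossary ties enrollment to informed consent, which comes before the start of treatment, and PFS is counted from the start of treatment.

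**Working it through.** The plan states no figure for this point, so the check is a comparison of texts plus simple counts.

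**1. Which texts point which way**

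| Reading | Supporting text |
|---|---|
| Stopping either drug is discontinuation | Protocol glossary entry. SAP 2.1.1.1 defines study treatment as the combination. Neither PFS section has a spartalizumab exemption, although the BOR sections do. |
| Only stopping both drugs is discontinuation | Amendment rationale, which names PFS. SAP 2.1.1.2 dates last study treatment by the last non-zero dose of either drug. Protocol 8.5.2.3 lists the end-of-treatment visit and the spartalizumab stop as alternatives. Protocol 9.1.1 ties discontinuation to the end-of-treatment visit, while Table 8-1b keeps subjects on capmatinib in the treatment period. |

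SAP 2.1.1.2 defines dates of administration, not discontinuation, so it supports the second reading without settling it.

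**2. What each document would do under the glossary reading**
- Protocol 12.5.2.1: censor at the last adequate scan before the spartalizumab stop.
- SAP 2.7.1: the stop followed the halt of 28-Jul-2021 and the amendment is dated 13-Oct-2021, 77 days after the halt. The stop therefore falls before approval and the parenthesis applies. Censoring is at the last adequate scan before approval of version 01, so scans up to approval are kept.

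The two documents would give different censoring dates for the same subject, while SAP Section 4 reports no change to the protocol-specified analyses.

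**3. How many subjects are exposed**
- Treated with the combination at the halt: 28. In screening, then started on capmatinib alone: 3. Total 28 + 3 = 31, which agrees with protocol 4.1.
- The 3 never received spartalizumab and are excluded from PFS, so the PFS population is 31 − 3 = 28.
- On capmatinib on 06-Sep-2021: 19. Between 0 and 3 of these are the capmatinib-only subjects.
- Combination subjects still on capmatinib on that date: 19 − 3 = 16 to 19 − 0 = 19. As shares, 16/28 = 57.1% and 19/28 = 67.9%.

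Under the full-stop reading, the sponsor's stop censors none of them.

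**4. The fallback date**
- Appendix 1 formula: time = end date − start date + 1, in days.
- Enrollment one day before first dose: −1 + 1 = 0 days.
- Enrollment 28 days before first dose, the limit of the screening window in protocol Section 8: −28 + 1 = −27 days. Protocol 6.3.1 allows enrollment at pre-screening, which could be earlier still.
- Start of treatment as end date: 0 + 1 = 1 day, as Appendix 1 requires.

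**The case against.** The strongest reply is that the plan, read as a whole, means a full stop. The amendment names PFS and this very event, and a study-specific statement should outweigh a general glossary line. Table 6-3 separates stopping spartalizumab from stopping study treatment, as do the places listed above. If the glossary governed, every combination subject would already have reached the end-of-treatment visit, which contradicts Table 8-1b and the continuing scan schedule. The SAP parenthesis also makes sense under a full stop: before the amendment, subjects who left treatment without progression went on being scanned, and the parenthesis keeps those scans up to approval. The missing PFS exemption is weak evidence, because the BOR wording sits in the primary estimand section and Part 1 no longer has a secondary estimand.

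Most of this stands. A reader might infer that the plan will censor every event-free combination subject and drop all later scans. The documents do not support that: they state the opposite intent, and even under the glossary reading the SAP keeps scans up to approval. A reader might also take 57% to 68% as the share of subjects losing events. It is not. Treatment beyond progression is allowed, so some of those on capmatinib may already have had their PFS event.

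What the reply leaves in place is that the only formal definition of the trigger conflicts with the stated intent, and that the rule to be programmed does not resolve the conflict.

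On the fallback date, it is fair to say that a subject censored at or before day 1 adds essentially no time at risk. The date is still wrong under either reading of the trigger.

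**Conclusion.** The trigger is an unreconciled definition, not a settled censoring of the whole PFS population. The harm is conditional on programming by the glossary. In that case, at most the 16 to 19 of 28 combination subjects still on capmatinib on 06-Sep-2021 are exposed, counted at that date, and only those without an event are affected. The number of events lost cannot be derived, because neither the approval date of version 01 nor the event status of these subjects is given.

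The enrollment fallback is an error under either reading: it can give times from 0 down to −27 days within the screening window. It barely moves the Kaplan-Meier estimates, and the number of subjects concerned is unknown.

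PFS in Part 1 is secondary, single-arm and descriptive. No test or primary result depends on it. Both points should be corrected before database lock, but neither undermines the study's main analysis.

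**What to change.** 1. In protocol 12.5.2.1 and SAP 2.7.1, including the SAP parenthesis, define the trigger as permanent discontinuation of all study drugs (capmatinib and spartalizumab).
2. In both places, state that stopping spartalizumab alone, for any reason including sponsor decision, is not a censoring reason for PFS, in line with the amendment rationale.
3. In both places, replace date of enrollment with date of start of treatment (duration = 1 day), as in Appendix 1.

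The cost is a few lines in the SAP with matching protocol text. No new data, visits or scans are needed. Under the SAP's own rules, a change before database lock is made by amendment.

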## 2.8 Safety analyses

The Safety set will be used for summaries and listings of safety data.

The overall observation period will be divided into 3 mutually exclusive segments:

***Pre-treatment period:***

- from day of subject's first informed consent to the day before first administration of study treatment

***On-treatment period:***

- from date of first administration of study drug to 30 days after the last actual administration of study treatment (including start and stop date)

***Post-treatment period:***

- Starting at date 31 after the last administration of study treatment

### 2.8.1 Adverse events (AEs)

Adverse event (AE) summaries will include all AEs occurring during on-treatment period. All AEs collected in the AE eCRF page will be listed along with the information collected on those AEs e.g., AE relationship to study drug, AE outcome etc. AEs starting during the post-treatment period will be flagged in the listings.

Adverse events (AEs) will be summarized by number and percentage of subjects having at least one AE, having at least one AE in each primary system organ class (SOC) and for each preferred term (PT) using MedDRA coding. A subject with multiple occurrences of an AE will be counted only once in the respective AE category. A subject with multiple CTCAE grades for the same preferred term will be summarized under the maximum CTCAE grade recorded for the event.

AE with missing CTCAE grade will be included in the 'All grades' column of the summary tables.

In AE summaries by primary SOC and PT, the primary SOC will be presented alphabetically and the PT will be sorted within primary SOC in descending frequency. Table by either primary SOC or PT will be sorted in descending frequency.

The following adverse event summaries will be produced for all subjects:

- Overview of adverse events summarized by relationship and deaths (number and % of subjects who died, with any AE, any SAE, fatal SAEs, AEs leading to dose reduction/interruptions, AE leading to treatment discontinuation)
- AEs by SOC and PT, summarized by relationship (all AEs and AEs related to study treatment).
- SAEs summarized by relationship (all SAEs and SAEs related to study treatment) and severity.
- AEs leading to study treatment discontinuation (all AEs and AEs related to study treatment).
- AEs leading to study treatment dose reduction/interruption.

The following listings will be produced:

- All adverse events (safety set)
- All serious adverse events (safety set) (including those from the pre and post-treatment periods)
- Adverse events among subjects who were not treated (screening failure subjects)

## **EudraCT and clinicaltrials.gov requirements for AEs and Deaths summaries**

For the legal requirements of clinicaltrials.gov and EudraCT, two required tables on on-treatment adverse events which are not serious adverse events with an incidence greater than 5% and on on-treatment SAEs and SAEs suspected to be related to study treatment will be provided by SOC and PT on the safety set population.

If for the same subject, several consecutive AEs (irrespective of study treatment causality, seriousness and severity) occurred with the same SOC and PT:

- a single occurrence will be counted if there is  $\leq 1$  day gap between the end date of the preceding AE and the start date of the consecutive AE
- more than one occurrence will be counted if there is  $> 1$  day gap between the end date of the preceding AE and the start date of the consecutive AE

For occurrence, the presence of at least one SAE / SAE suspected to be related to study treatment / non-SAE has to be checked in a block e.g., among AEs in a  $\leq 1$  day gap block, if at least one SAE is occurring, then one occurrence is calculated for that SAE.

The number of deaths resulting from SAEs suspected to be related to study treatment and SAEs irrespective of study treatment relationship will be provided by SOC and PT.

## 2.8.1.1 Adverse events of special interest / grouping of AEs

An adverse event of special interest (AESI) is a grouping of adverse events that are of scientific and medical concern specific to spartalizumab and/or capmatinib. These groupings are defined using MedDRA terms, SMQs (standardized MedDRA queries), HGLTs (high level group terms), HLT (high level terms) and PTs (preferred terms). Customized SMQs (Novartis MedDRA queries, NMQ) may also be used. A NMQ is a customized group of search terms which defines a medical concept for which there is no official SMQ available or the available SMQ does not completely fit the need. It may include a combination of single terms and/or an existing SMQ, narrow or broad.

For each specified AESI for each study drug, the number and percentage of subjects with at least one event of the AESI occurring during on-treatment period will be summarized for each study drug separately:

- Overview of adverse events of special interest for capmatinib
- Overview of adverse events of special interest for spartalizumab

A listing of all grouping levels down to the MedDRA preferred terms used to define each AESI will be generated.

Note: From the eCRS, only risk where “Core Safety Risk” = Y should be selected to report Adverse events of special interest in the CSR (the variable name in GPS, for “Core Safety Risk”, is SP).

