## Study Update

As of 28-Jul-2021 when enrollment was halted, 28 patients were treated with capmatinib plus spartalizumab and 3 patients were in screening in the run-in part (Part 1) of the study. The patients who were on combination treatment have discontinued spartalizumab and are continuing on capmatinib single agent since the enrollment halt. The patients who were in screening at the time of the enrollment halt have started receiving capmatinib single agent treatment. As of 06-Sep-2021, 19 patients were still on treatment with capmatinib.

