#### Part 1: Single Arm Run-in Part

Part 1 of the study was designed to assess the efficacy and safety of capmatinib in combination with spartalizumab in treatment-naive adult subjects with advanced NSCLC harboring METΔex14 mutation. Based on the safety observed during Part 1, the decision was made not to open Part 2.

Thirty-one patients were treated in Part 1 of the study.

The primary objective of Part 1 of the study is to evaluate the anti-tumor activity of capmatinib in combination with spartalizumab. The primary outcome measure of anti-tumor activity is ORR according to RECIST 1.1 and as determined by investigator assessment. ORR is an endpoint that can be used to assess earlier the efficacy of a treatment in studies with small sample size ([FDA-industry guidance 2018](#)). Given the efficacy observed with capmatinib single agent in the same patient population ([Anon 2019](#), [Wolf et al 2019](#)), ORR can be used as a surrogate endpoint to predict the clinical benefit of capmatinib in combination with spartalizumab in the context of the single arm run-in part of the study ([FDA-industry guidance 2015](#)).

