## 2 Statistical methods

### 2.1 Data analysis general information

Study data will be analyzed by Novartis personnel using the most updated SAS® version in the GPS environment. For analyses using R and/or JAGS (e.g., Bayesian analysis) in the DaVinci environment will be used. PK parameters will be calculated using non-compartmental methods available in the most updated version of Phoenix WinNonlin.

Data from all participating centers in this protocol will be combined by part, so that an adequate number of subjects will be available for analysis. Data will be summarized using descriptive statistics (continuous data) and/or contingency tables (categorical data) for demographic and baseline characteristics, efficacy, safety, pharmacokinetic and pharmacodynamics measurements.

Study data in Part 1 will be reported in the final clinical study report (CSR) based on all subjects' data up to the time of completion of the study. There will be no additional CSR. The final CSR will include all outputs planned within the TFL shells document.

The part 1 of this study has one treatment arm: capmatinib + spartalizumab

**Qualitative data** (e.g., gender, race, etc.) will be summarized by means of contingency tables; a missing category will be included as applicable. Percentages will be calculated using the number of patients in the relevant population or subgroup as the denominator.

**Quantitative data** (e.g., age, body weight, etc.) will be summarized by appropriate descriptive statistics (i.e., mean, standard deviation, median, minimum, and maximum).

Screen failure patients are those who signed the informed consent, but never started the study treatment for any reason. For these patients, the eCRF data collected will not be included in analyses but will be reported in the CSR as separate listings.

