## 2.2 Analysis sets

### Full Analysis Set (FAS)

The Full Analysis Set (FAS) comprises all subjects to whom study treatment has been assigned and who received at least one dose of study treatment (i.e., at least one dose of any component of the study treatment that is capmatinib or spartalizumab (including incomplete infusion)).

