### Safety Analysis Set (SS)

The FAS and Safety Set are identical.

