### 2.5.2 Statistical hypothesis, model, and method of analysis

Overall response rate (ORR) by investigator assessment is calculated based on the data from the FAS and the corresponding 95% CI based on the exact binomial distribution ([Clopper and Pearson 1934](#)) will be presented.

Participants who had never received one of the investigational drugs will be excluded from the efficacy analysis.

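### Spartalizumab-specific safety and dosing summaries appear to use all 31 treated subjects, although only 28 received spartalizumab; separately, the SAP 2.8.3 liver groups omit subjects with one raised baseline enzyme

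*SAP*

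**What the plan says.** **Who was treated.** The Study Update in the protocol amendment counts 28 subjects on both drugs and 3 in screening at the enrollment halt. It adds: "The patients who were in screening at the time of the enrollment halt have started receiving capmatinib single agent treatment". Protocol 4.1 gives the total: "Thirty-one patients were treated in Part 1 of the study".

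**Who is in the Safety Set.** SAP 2.2 admits to the Full Analysis Set anyone assigned treatment who received "at least one dose of any component of the study treatment that is capmatinib or spartalizumab (including incomplete infusion", and then states: "The FAS and Safety Set are identical". The Safety Set is used for all safety data (SAP 2.8) and all study-treatment summaries (SAP 2.4.1).

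**How results are laid out.** SAP 2.1 says: "The part 1 of this study has one treatment arm: capmatinib + spartalizumab". Subgroups are not applicable (SAP 2.2.3). SAP 2.8.1 opens its list of tables with: "The following adverse event summaries will be produced for all subjects". For AESIs, SAP 2.8.1.1 says that "the number and percentage of subjects with at least one event of the AESI occurring during on-treatment period will be summarized", with one overview for each drug.

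**Where the 3 are excluded.** SAP 2.5.2 says: "Participants who had never received one of the investigational drugs will be excluded from the efficacy analysis". SAP 2.7.1 repeats the rule for disease control rate and PFS. No such rule appears for adverse events, laboratory data or dosing.

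**Dose of a drug never taken.** SAP 2.4.1.2 assigns a cumulative dose of zero for the drug concerned. SAP 2.4.1.3 assigns a zero dose intensity (DI) but does not tie it to a particular drug. SAP 2.4.1.1 starts spartalizumab exposure at the first non-zero spartalizumab dose.

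**Liver table.** SAP 2.8.3 defines two baseline groups for the combined transaminase-bilirubin rows: AST and ALT both within the upper limit of normal (ULN), and AST and ALT both above it.

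**The concern.** Enrollment stopped because the combination was poorly tolerated, and the SAP's safety objective concerns the combination. A reader will therefore want event rates and dosing in the subjects who received both drugs. On the SAP text, no AE table isolates those 28.

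The problem is sharpest where a summary is about spartalizumab itself. A subject never given the drug cannot have an adverse effect of it and has no dosing history for it. Counting such subjects dilutes the percentage, or credits spartalizumab with an event that arose on capmatinib alone. In the dosing tables, zeros that reflect a sponsor decision could be read as poor tolerability. The SAP saw the same issue for efficacy and dealt with it there.

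The liver grouping is a separate matter. A subject with one raised baseline enzyme who later met the combined criteria would be counted in no combined row.

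**Working it through.** **1. The documents' own count.** 28 (both drugs) + 3 (capmatinib only) = 31, which matches Protocol 4.1. Never exposed to spartalizumab: 3/31 = 9.7% of the Safety Set.

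**2. AESI percentages.** Let x be the number of the 28, and j the number of the 3, with a given spartalizumab AESI.

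- Exposed rate: x/28.
- Rate on the Safety Set: (x+j)/31, with j from 0 to 3.
- With j = 0, the ratio of the second to the first is 28/31 = 0.903.
- The pooled rate exceeds the exposed rate when j/3 > x/28, so the direction is not fixed.

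Illustrative counts, not trial data:

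| x | x/28 | x/31 (j = 0) | (x+3)/31 (j = 3) |
|---|---|---|---|
| 0 | 0% | 0% | 9.7% |
| 3 | 10.7% | 9.7% | 19.4% |
| 7 | 25.0% | 22.6% | 32.3% |
| 14 | 50.0% | 45.2% | 54.8% |
| 28 | 100% | 90.3% | 100% |

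The largest possible gap is 9.7 percentage points either way (x = 28 with j = 0, or x = 0 with j = 3).

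**3. Spartalizumab cumulative dose.** If SAP 2.4.1.2 is read naturally, three zeros enter the summary.

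- Mean: 28/31 = 0.903 times the mean in the 28.
- Minimum: 0.
- Median: the 16th of 31 ordered values. With three zeros placed first, that is the 13th of the 28 values, instead of the average of the 14th and 15th.

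**4. Spartalizumab DI.** Zero is the likely reading of SAP 2.4.1.3 but not a certain one, because these 3 subjects did take a drug. If it is zero, and if all 28 received exactly 400 mg/cycle (an assumption made to show the scale):

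- Mean = 28 × 400/31 = 361.3 mg/cycle.
- Sample SD = 400 × √(28 × 3/(31 × 30)) = 120.2, instead of 0.
- Median = 400; minimum = 0.

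**5. Relative dose intensity (RDI).** RDI is DI divided by planned DI, and planned DI divides by exposure duration. The 3 have no spartalizumab exposure duration, so RDI is undefined for them and the SAP gives no rule.

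**6. Interruptions.** SAP 2.4.2 defines an interruption as a zero dose lying between non-zero doses. The 3 cannot have a spartalizumab interruption, so on a denominator of 31 that percentage is always 0.903 times the exposed one.

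**7. Liver rows.** Each baseline group has three combined rows, so there are 3 + 3 = 6. A subject with exactly one enzyme above ULN at baseline is in neither group and so in none of the six. The footnote to the second group sets a threshold for an enzyme that was normal at baseline. If both enzymes must be raised to enter that group, this branch can never apply. Inclusion criterion 8 (Protocol 5.1) admits subjects with raised baseline enzymes, so the case can arise.

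**The case against.** **The pooling is specified in the protocol.** Protocol 9.1.1.1 has every treated subject contribute to the final analyses. Protocol section 12 runs all analyses on all subjects, 12.1 defines the Safety Set by any component, 12.5.2.2 applies it to all safety analyses, and 12.3 applies it to exposure, DI and RDI. The amendment limited the exclusion to efficacy, and the SAP follows. This stands. A reader might infer that the N=31 safety tables are wrong or contradict the protocol; they are not and do not.

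**The denominator of 31 is inferred.** SAP 2.1 takes percentages on the population or subgroup concerned, SAP 2.8.1.1 reports AESIs drug by drug, and the table shells, which could set another denominator, are separate documents not seen here. This stands as a limit. But no exposed-only set or subgroup is defined, and reporting by drug separates the AESI lists without restricting who is counted. So 31 remains the most natural reading.

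**The dose mean is not certain to be understated.** SAP 2.4.1.2 assigns a value but does not say whether never-exposed subjects enter the summary. This stands: zero is the natural reading only.

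**The on-treatment window is no error.** AEs are collected to 150 days after spartalizumab, but tables stop 30 days after the last dose of study treatment. A reader might infer that late immune-related events are lost. The window is the protocol's own, later events are listed and flagged, and all deaths are tabulated. What remains is that SAP 2.1.1.6 promises combined-period summaries of related AEs which 2.8.1 does not name.

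**The effect is modest.** Three of 31 subjects are involved in a descriptive study, and listings would let a reader separate the 28. This is fair, and it limits the weight of the point.

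**Conclusion.** The point holds for spartalizumab-specific summaries. As the SAP reads, 31 is the most natural denominator for spartalizumab AESIs although 28 subjects were exposed. If the 3 have no event, each percentage is 0.903 times the exposed rate; otherwise it can reach (x+3)/31. It would be wrong to conclude that spartalizumab AESI rates are necessarily understated, because an event in a capmatinib-only subject can raise them.

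For dosing, cumulative dose would take in three zeros on the natural reading, DI probably would, and RDI has no rule. These conclusions assume that the shells do not already restrict the spartalizumab tables and that the 3 never received spartalizumab later, which agrees with its discontinuation in all ongoing subjects. No exposed-only AE table is named. Adding one supplements the protocol's all-treated tables and does not correct them.

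The liver grouping in SAP 2.8.3 is a separate drafting slip. It affects only the six combined rows; the single-parameter ALT/AST and bilirubin rows still count every subject.

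**What to change.** 1. **Dosing (SAP 2.4.1 and 2.4.2).** State that spartalizumab exposure, cumulative dose, DI, RDI, interruptions and discontinuations are summarized in subjects with at least one spartalizumab dose. This replaces the Safety Set named in Protocol 12.3, so record it in SAP section 4, which now reports no changes.
2. **AESIs and AEs (SAP 2.8.1 and 2.8.1.1).** Use spartalizumab-exposed subjects as the denominator of the spartalizumab AESI table, and mention this in the same section 4 entry, since Protocol 12.5.2.2 applies the Safety Set to all safety analyses. Keep the N=31 AE tables, add AE and SAE tables for the 28, and list the 3 capmatinib-only subjects separately. The capmatinib AESI table stays on 31, as all 31 received capmatinib.
3. **Liver table (SAP 2.8.3), separate item.** Define the second baseline group as AST or ALT above ULN. Subjects with one raised enzyme then enter it, and the footnote's first branch can apply.
4. **Detail.** Name in 2.8.1 the combined-period related-AE tables promised in 2.1.1.6. A table of spartalizumab AESIs in the 28 up to 150 days after the last infusion would be an optional supplement.

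The cost is SAP and shell edits and a few extra tables. No new data are needed, and the definitions of the Safety Set and the on-treatment period do not change.
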